8.3.2 DEFINITION OF SERIOUS ADVERSE EVENTS (SAE)

An SAE includes any event that results in any of the following outcomes:

- Death
- Life-threatening event (i.e., the subject was, in the opinion of the investigator, at immediate risk of death from the event as it occurred. It does not apply to an AE that hypothetically might have caused death if it were more severe.)
- Persistent or significant disability/incapacity or substantial disruption of the subject's ability to carry out normal life functions
- Requires in-patient hospitalization or prolongs hospitalization (i.e., a prolonged hospitalization beyond the expected length of stay; hospitalizations for elective medical/surgical procedures, scheduled treatments, or routine check-ups are not SAEs by this criterion)
- Congenital anomaly/birth defect (i.e., an adverse outcome in a child or fetus of a subject exposed to the molecule or investigational product before conception or during pregnancy)
- Does not meet any of the above serious criteria but based upon investigator's clinical judgment put the subject at significant risk of morbidity or death or may require medical or surgical intervention to prevent one of the outcomes listed above (i.e., is a significant or important medical event)

8.3.3 CLASSIFICATION OF AN ADVERSE EVENT

8.3.3.1 SEVERITY OF EVENT

The investigator is responsible for evaluating all AEs and determining the severity of the event. Severity will be categorized as mild, moderate, or severe according to the following definition:

- **Mild:** Event may be noticeable to subject; does not influence daily activities; usually does not require intervention
- **Moderate:** Event may be of sufficient severity to make a subject uncomfortable; performance of daily activities may be influenced; intervention may be needed
- **Severe:** Event may cause severe discomfort; usually interferes with daily activities; subject may not be able to continue in the study; treatment or other intervention usually needed

8.3.3.2 RELATIONSHIP TO STUDY INTERVENTION

Relationship of an AE to investigational product will be assessed as follows:

- **Definite:** There is a clinically plausible time sequence between the onset of the AE and the administration of investigational product; when the event responds to withdrawal of investigational product and recurs with re-administration of investigational product
- **Probable:** There is a clinically plausible time sequence between the onset of the AE and the administration of investigational product; the AE is unlikely to be caused by the concurrent/underlying illness, other drugs or procedures
- **Possible:** There may or may not be a clinically plausible time sequence between the onset of the AE and the administration of investigational product and a cause cannot be ruled out
- **Unrelated:** There is not a temporal or causal relationship to investigational product administration

8.3.3.3 EXPECTEDNESS

The Sponsor medical monitor will be responsible for determining whether an AE is expected or unexpected. An unexpected AE is one not identified in nature, severity, or frequency in the current protocol or Investigator's Brochure.

8.3.4 TIME PERIOD AND FREQUENCY FOR EVENT ASSESSMENT AND FOLLOW-UP

8.3.4.1 FOLLOW-UP OF NON-SERIOUS ADVERSE EVENTS

Non-serious AEs that are identified during the last scheduled study visit must be recorded on the AE eCRF as ongoing. If the non-serious AE is dysphagia or the non-serious AE is determined to be related to study treatment by the investigator, the subject should be followed until the dysphagia or drug-related AE resolves, returns to the pre-treatment status, or determines by the investigator to be stable.

Any clinically significant abnormal test results (e.g., laboratory findings, ECG findings) at the final assessment should be followed to resolution or until determined by the investigator to be stabilized. Repeat tests may be indicated to establish this.

If a subject has any clinically significant lab abnormalities at the end of the study, the medical monitor should be notified, and every effort made by the investigator to arrange follow up evaluations at appropriate intervals to document the course of the lab abnormalities.

8.3.4.2 FOLLOW-UP OF POST STUDY SERIOUS ADVERSE EVENTS

SAEs that are identified on the last scheduled contact must be recorded on the AE eCRF page and reported to the sponsor or the authorized representative according to the reporting procedures outlined in **Section 8.3.6**. This may include unresolved previously reported SAEs, or new SAEs. The investigator should follow the SAE until it resolves or is determined by the investigator to be stable, or the subject is lost to follow-up. The investigator should continue to report any significant follow-up information to the sponsor or the authorized representative, and the IRB/REB/EC, up to the point the event has resolved or is determined to be stable. Resolution means the subject has returned to the baseline state of health, and stable means the investigator does not expect any further improvement or worsening of the subject's condition.

Any new SAEs reported by the subject to the investigator that occur after the last scheduled contact and are determined by the investigator to be reasonably associated with the administration of investigational product should be reported to the sponsor or the authorized representative, and the IRB/REB/EC, as required.

8.3.5 ADVERSE EVENT REPORTING

The investigator will assess subject post-treatment and at each subsequent study visit for the occurrence of AEs. In order to avoid bias in eliciting AEs, subjects should be asked the following non-leading question: "How have you felt since your last visit?" All AEs (serious and non-serious) reported by the subject must be recorded on the source documents and eCRFs.

8.3.6 SERIOUS ADVERSE EVENT REPORTING

An investigator must report an SAE to the sponsor or the authorized representative within **24 hours** of their awareness of the event:

1. Complete and return an SAE Form with all information known to date; including the investigator's assessment of causality.
2. If the event is fatal or life-threatening, telephone the sponsor or the authorized representative as soon as the investigator learns of the event.
3. Obtain and maintain all pertinent medical records (discharge summary, autopsy report, etc.) and clinical judgments of medical personnel who assisted in subject's treatment and follow-up.
4. Provide follow-up information to the sponsor or the authorized representative.

Regulatory authorities, IRBs/REBs/ECs, and investigators will be notified of SAEs in accordance with applicable regulations and requirements (e.g., GCPs, ICH Guidelines, national regulations and local requirements).

The investigator will collect information on SAEs until subject's health has returned to baseline, the SAE has stabilized, or remaining health issues have otherwise been explained.

8.3.7 REPORTING EVENTS TO PARTICIPANTS

The sponsor will disclose clinical trial data to individuals, to investigators at clinical sites, and publicly as aggregate summaries, in accordance with applicable regulations and requirements.

8.3.8 EVENTS OF SPECIAL INTEREST

8.3.8.1 CLINICAL DIAGNOSTIC CRITERIA FOR ANAPHYLAXIS QUERY

Anaphylaxis is highly likely when any *one (1)* of the following three (3) criteria are fulfilled:
(*Sampson et al., 2006*)

1. Acute onset of an illness (minutes to several hours) with involvement of the skin, mucosal tissue, or both (e.g., generalized hives, pruritus or flushing, swollen lips-tongue-uvula)

[figure not shown]
And at least *one (1)* of the following
 - a. Respiratory compromise (e.g., dyspnea, wheeze-bronchospasm, stridor, reduced PEF, hypoxemia)
 - b. Reduced BP or associated symptoms of end-organ dysfunction (e.g., hypotonia [collapse], syncope, incontinence)
2. Two (2) or more of the following that occur rapidly after exposure to a likely allergen for that subject (minutes to several hours):
 - a. Involvement of the skin-mucosal tissue (e.g., generalized hives, itch-flush, swollen lips-tongue-uvula)
 - b. Respiratory compromise (e.g., dyspnea, wheeze-bronchospasm, stridor, reduced peak expiratory flow, hypoxemia)
 - c. Reduced BP or associated symptoms (e.g., hypotonia [collapse], syncope, incontinence)
 - d. Persistent gastrointestinal symptoms (e.g., crampy abdominal pain, vomiting)
3. Reduced BP after exposure to known allergen for that subject (minutes to several hours):
 - a. Adults: systolic BP of less than 90 mm Hg or greater than 30% decrease from that person's baseline

[REDACTED]

[REDACTED]

[REDACTED]

[REDACTED]

- [REDACTED]
- [REDACTED]
- [REDACTED]
- [REDACTED]
- [REDACTED]

[REDACTED]

[REDACTED]

8.3.9 REPORTING OF PREGNANCY

During the trial, all WOCBP should be instructed to contact the investigator immediately (within 24 hours) if they suspect they might be pregnant (e.g., missed or late menstrual cycle). The investigator must immediately notify the sponsor or the authorized representative of any female subject who becomes pregnant any time during study participation, record the information on the Pregnancy Notification Form and send the form to the authorized representative. The site will be asked to follow-up with the subject periodically during the pregnancy for ongoing health and safety information through term, as applicable. Subjects who become pregnant during the study will not be discontinued from the study, but will NOT receive additional treatment in the study.

8.4 UNANTICIPATED PROBLEMS

8.4.1 DEFINITION OF UNANTICIPATED PROBLEMS

In accordance with the Office for Human Research Protections (OHRP), FDA final rule and the European Union Directive 2001/20/EC, unanticipated problems (UPs) will be defined as follows:

- Untoward and unintended responses to an investigational medicinal product related to any dose administered
- Unexpected in terms of the nature or severity of which is not consistent with the applicable product information (e.g. investigator's brochure for an unauthorised investigational product or summary of product characteristics for an authorised product)
- Serious in that it results in death, is life-threatening, requires hospitalisation or prolongation of existing hospitalisation, results in persistent or significant disability or incapacity, or is a congenital anomaly or birth defect
- A reasonable possibility of a causal relationship between the event and the investigational medicinal product (IMP). This means that there are facts (evidence) or arguments to suggest a causal relationship

8.4.2 UNANTICIPATED PROBLEM REPORTING

The investigator will report UPs to the reviewing IRB/REB/EC and sponsor. The UP report will include the following information:

- Protocol identifying information: protocol title and number, PI's name, and the IRB/REB/EC project number;
- A detailed description of the event, incident, experience, or outcome;
- An explanation of the basis for determining that the event, incident, experience, or outcome represents an UP;
- A description of any changes to the protocol or other corrective actions that have been taken or are proposed in response to the UP.

To satisfy the requirement for prompt reporting, UPs will be reported using the following timeline:

- Unanticipated problems that are SAEs will be reported to the Regulatory Authorities and IRB/REB/EC, in accordance with applicable regulations and requirements, within **7 days** and to the sponsor within **24 hours** of the investigator becoming aware of the event.
- Any other UP will be reported to the Regulatory Authorities and IRB/REB/EC, in accordance with applicable regulations and requirements, within **14 days** and to the sponsor within **14 days** of the investigator becoming aware of the problem.

All suspected unexpected serious adverse reactions (SUSARs) will be reported in compliance with the requirements of the respective Regulatory Authority.

8.4.3 REPORTING UNANTICIPATED PROBLEMS TO PARTICIPANTS

The sponsor will disclose clinical trial data to individuals, to investigators at clinical sites, and publicly as aggregate summaries, in accordance with applicable regulations and requirements.

[figure not shown]
8.5 EFFICACY ASSESSMENTS

As part of study preparations, investigators will receive standardized training on the efficacy assessments in this study. It is recommended that the same investigator perform all efficacy assessments for a given subject from Baseline to end of study.

[REDACTED]

[REDACTED]

[REDACTED]

9 STATISTICAL ANALYSIS

All statistical analyses will be performed using Statistical Analysis Software (SAS[®]) version 9.3 or higher. A statistical analysis plan (SAP) will be created during the study conduct.

Efficacy and safety data will be summarized with descriptive statistics. Multiple imputation with MMRM will be used to impute the missing TWSTRS-total scores up to subject discontinuation or completion. In the case a subject is lost to follow-up, no imputation will be done beyond their last date of contact. No imputations will be made for safety or efficacy data other than the TWSTRS-total score.

Efficacy endpoint based on the Total TWSTRS will be summarized for the ITT (multiple imputation) and for PP populations. All other efficacy endpoints will be summarized for the ITT (observed cases) and for PP populations.

Safety data will be summarized for the safety population.

9.1 SAMPLE SIZE JUSTIFICATION

The sample size for this study is based on a requirement from Regulatory Authorities to collect safety data on approximately 350 subjects treated once and long-term safety data on at least 100 adult subjects with isolated cervical dystonia treated with 3 or 4 continuous treatment cycles of low-dose or high-dose DAXI for injection, with at least 50 subjects treated with the high-dose DAXI for injection for 3 or 4 continuous treatment cycles. [REDACTED]

[REDACTED]

[REDACTED]

[REDACTED]

[REDACTED]

[REDACTED]

[REDACTED]

[REDACTED]

9.3 PRIMARY STUDY OBJECTIVES AND ENDPOINTS

Primary Objectives:

- To evaluate the long-term safety of multiple continuous treatments of DAXI for injection
- To assess immunogenicity to BoNTA and RTP004 after multiple treatments of DAXI for injection

Primary Endpoints:

[figure not shown]
- Dose- and cycle-specific incidence of drug-related adverse events
- Dose- and cycle-specific incidence of drug discontinuation due to drug-related AEs
- Dose- and cycle-specific incidence of immunogenicity

[REDACTED]

[REDACTED]

- [REDACTED]
- [REDACTED]
- [REDACTED]

[REDACTED]

- [REDACTED]
- [REDACTED]
- [REDACTED]
- [REDACTED]
- [REDACTED]
- [REDACTED]

9.6 PLANNED ANALYSES

All efficacy endpoints, including responder rates, will be summarized with descriptive statistics by dose and/or treatment cycle, unless otherwise specified.

Discontinuation rate will be summarized by dose and cycle as well as overall. Additionally, the number of weeks on study will be summarized with descriptive statistics.

Duration of effect after each treatment, defined as time (number of weeks) from treatment until loss of 80% of the peak treatment effect (i.e., the average of the change from baseline in the TWSTRS-total score at Weeks 4 and 6)

[figure not shown]
- If a subject has no reduction in the TWSTRS-total score at Week 4 and Week 6, his/her duration of effect will be set to 0. If a subject discontinues or withdraws from the study prior or at Week 6, his/her duration of effect will be set to 0.
- If a subject discontinues or withdraws from the study prior to reaching his/her target TWSTRS score at any visit after Week 6, his/her duration of effect will be censored at the last visit. If a subject rolled over from Study Protocol 1720302 at Week 36 prior to reaching his/her target TWSTRS score, his/her duration will be calculated from the injection date in Study Protocol 1720302 to the time his/her TWSTRS-total score reaches/exceeds the target TWSTRS score.

Kaplan-Meier survival curves will be plotted for each dose level for the time-to-event endpoints. Point estimate of median duration and 2-sided, 95% confidence intervals (CIs), will be generated using the log-rank test. A subject might be counted more than once or in multiple groups due to multiple injections cycle. Exploratory statistical comparisons between subgroups and duration of response evaluation may be performed.

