4.3 STUDY VISITS AND TELEPHONE CALLS

[figure not shown]
Figure 3 summarizes the schedule of telephone calls and assessments by treatment cycle.

[figure not shown]
- Screening (Days -21 to -1)
- Baseline Treatment #1, Treatment #2, #3, #4
- Follow-up telephone call after each Treatment:
 - Week 2 after each treatment (study site staff will call the subject)
- Follow-up visits after each Treatment:
 - Weeks 4, 6, 12, and every 4 weeks thereafter until Week 52/End-of-Study Visit (See Figure 1 and Table 1)

[figure not shown]
Safety assessments include laboratory tests (hematology, PT, chemistry, and urinalysis), [REDACTED], [REDACTED], physical and neurological examinations, the C-SSRS, Dysphagia Severity Scale, vital signs, pulmonary function by spirometry, 12-lead ECGs, injection site evaluations, concomitant medications, AE monitoring at protocol-specified timepoints, [REDACTED]

Efficacy assessments, including the TWSTRS (total score and subscale scores), CDIP-58, CGIC, PGIC, TSQ, WPAI, and SF-36 Survey, will be performed at protocol-specified timepoints as outlined in the SOA (Table 1).

No interim analysis is planned for this study.

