8.1.3 VARIATION FROM SCHEDULED VISIT DAYS

To allow for scheduling flexibility, limited variation will be permitted from the specified time of each visit (Table 3).

Table 3. Allowed Variation from Scheduled Visit Days

Scheduled Visit After Each Treatment	Allowed Variation (calendar days)
Weeks 4 and 6	± 3 days
Weeks 12, 16, 20, 24, 28, 32, 36, 40, 44, 48, and 52/EOS	± 6 days
Treatment #2, #3, and #4	± 14 days

Note: Two weeks after each Treatment (at Week 2 [allowed variation: ± 3 days]), the subject will be contacted by telephone to follow up on clinical effect, any AEs or changes in concomitant medications.

A subject who experiences significant recurrence of CD symptoms (e.g. pain) during the study before his/her TWSTRS-total score reaches the target TWSTRS score may request another treatment before the next scheduled visit. In this case, the subject may have an unscheduled visit for the investigator to assess whether another treatment is warranted based on the subject's symptoms and neurologic exam findings. If the investigator confirms that retreatment is clinically indicated, the subject may receive another treatment at this visit, unless less than 12 weeks have passed since the last injection or the injection will occur after Week 40 (i.e., there is less than 12 weeks of follow up left in the 52-week study period).

Note: After each Treatment, study visits are reset to begin from that Treatment to Week 4, Week 6, Week 12, and every 4 weeks thereafter.

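### Loss of effect is seen only at visits 6 and then 4 weeks apart; the ordinary Kaplan-Meier analysis in the visible plan would date detected losses about 2 weeks late on average

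*Protocol*

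**What the plan says.** Protocol section 9.6 describes duration of effect after each treatment as "defined as time (number of weeks) from treatment until loss of 80% of the peak treatment effect", where the peak is the average change in TWSTRS-total at Weeks 4 and 6. It gives three further rules:

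- Duration is 0 for a subject with no reduction at Weeks 4 and 6, or who leaves at or before Week 6.
- A subject who leaves after Week 6 without reaching target is censored at the last visit.
- For subjects who rolled over from 1720302 at Week 36, duration runs from the injection date in that study "to the time his/her TWSTRS-total score reaches/exceeds the target TWSTRS score".

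The method is stated as "Kaplan-Meier survival curves will be plotted for each dose level for the time-to-event endpoints", with a median and two-sided 95% confidence interval.

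On visits, Protocol section 4.3 schedules follow-up after each treatment at "Weeks 4, 6, 12, and every 4 weeks thereafter until Week 52/End-of-Study Visit"; the Week 2 contact is a telephone call. Section 8.1.3 adds that "After each Treatment, study visits are reset to begin from that Treatment to Week 4, Week 6, Week 12, and every 4 weeks thereafter". Its Table 3 allows 3 days either way at Weeks 4 and 6, and 6 days either way at "Weeks 12, 16, 20, 24, 28, 32, 36, 40, 44, 48, and 52/EOS". If symptoms recur before target is reached, "the subject may have an unscheduled visit for the investigator to assess whether another treatment is warranted".

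SAP section 6.4 says that analyses in general follow the nominal visit label; the text after that is redacted. The duration analysis in SAP section 8 is not visible. SAP section 10 drops multiple imputation, and its visible text brings in no interval-censored method. No visible sentence says whether the event time is the visit date, the nominal week or an interpolated time.

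**The concern.** The event is a score crossing a threshold, and that happens between visits. All that is known is that it came after the last visit below target and no later than the first visit at or above it. Ordinary Kaplan-Meier needs a single time. Section 9.6 has rules for zeros and for right-censoring but none for this interval, so the default is the detecting visit. Recorded durations then include the wait for that visit, and the curve reflects the visit calendar as well as the drug.

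At stake is how a reader takes the reported median in weeks and its confidence interval. A median that is late by an amount depending on where it falls between visits, with an interval that does not reflect this, could be read as more precise and longer than the data support.

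**Working it through.** There is no figure in the plan to reproduce. The visible text gives no expected duration or precision target, and the sample size (about 350 treated once, at least 100 with 3 or 4 cycles) is a regulatory exposure requirement.

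**1. Gaps (Protocol sections 4.3 and 8.1.3).** Weeks 6 to 12: 12 − 6 = 6 weeks. From Week 12: 16 − 12 = 4 weeks, and so on. With the Table 3 windows, a nominal 28-day gap can run from 28 − 12 = 16 to 28 + 12 = 40 days, and the 42-day gap from 42 − 9 = 33 to 42 + 9 = 51 days. One missed visit makes a gap of 4 + 4 = 8 weeks, or 16 − 6 = 10 weeks if Week 12 is missed.

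**2. Average delay.** If the crossing is uniform within a gap of width w, dating it at the right end adds w/2 on average, with range 0 to w. This gives 4/2 = 2 weeks and 6/2 = 3 weeks.

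**3. Simulated delay.** The documents give no distribution, so one is assumed: log-normal true durations, medians 12 to 28 weeks, log-SD 0.35 and 0.5, restricted to 6 to 52 weeks, each moved to the first visit at or after the crossing. Selected rows, log-SD 0.35, in weeks:

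| True median | Mean delay, nominal weeks | Reported median, nominal | Median shift, nominal | Median shift, actual dates |
|---|---|---|---|---|
| 12.1 | 2.40 | 16.0 | 3.9 | 3.1 |
| 14.1 | 2.19 | 16.0 | 1.9 | 2.1 |
| 16.0 | 2.08 | 20.0 | 4.0 | 3.1 |
| 18.0 | 2.04 | 20.0 | 2.0 | 2.1 |
| 20.0 | 2.02 | 20.0 | 0.0 | 0.9 |
| 23.9 | 2.00 | 24.0 | 0.1 | 0.9 |

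Over all scenarios:
- The mean delay is 1.99 to 2.50 weeks on nominal weeks, and 2.06 to 2.53 with visits spread over their windows.
- Individual delays on the nominal grid run from 0 to 6 weeks (SD 1.2 to 1.5). Only 22% to 25% lie between 1.5 and 2.5 weeks.
- The median shift is 0.0 to 4.0 weeks on nominal weeks and 0.9 to 3.1 with actual dates.
- Weibull durations (shape 2 or 3, medians 14 to 24, also assumed) give a mean delay of 2.0 to 2.2 weeks overall and 2.4 to 2.9 for losses between Weeks 6 and 12.

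**4. Median.** On nominal weeks, a true median m in a gap ending at b is reported as b, so the shift is b − m: 16 − 14 = 2, but 16 − 15.9 = 0.1. A true median on a visit week is a knife-edge, which is why the 16.0 and 20.0 rows differ so much. In groups of 101, such a median is reported at that week about half the time and 4 weeks higher the other half. In 1,000 Kaplan-Meier samples of 100 subjects (10% zeros and random censoring, both assumed), every median on nominal weeks was 16, 20 or 24. With actual dates only about 7% fell exactly on a scheduled week, though they still clustered near those weeks.

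**5. Score noise.** With a 12-point linear loss from Week 6 to the crossing and visit-to-visit noise of SD 0, 2 or 4 points (assumed), the mean delay is 2.0, 1.6 and 0.3 weeks. Noise makes some scores reach target early.

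**The case against.** The strongest objection is that the event-time convention is inferred. The section that would state it is redacted, and a rule may exist there. That stands, and it limits the point to the visible plan. It is also fair that duration is not among the primary endpoints (drug-related adverse events, discontinuation because of them, immunogenicity), that the study is open-label with descriptive efficacy summaries, and that comparisons are exploratory and optional. All doses share one visit grid, so they shift in the same direction. Score noise can remove much of the shift, and the Turnbull median is generally an interval, so any gain in precision depends on a stated interpolation rule.

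Several stronger readings are tempting but not supported:

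- *Every duration is about 2 weeks too long.* Zeros do not move, withdrawals are right-censored, and 2 weeks is only an average over detected losses.
- *The median can fall only on a visit week.* This is true for nominal weeks. SAP section 6.4 leans that way in general, but Protocol section 9.6 counts the rollovers from the injection date, and windows and unscheduled visits spread actual dates.
- *Remote visits in the COVID-19 period widen the gap.* SAP section 8.3 summarises remote TWSTRS scores, so only a missed visit does this.
- *Subjects who ask for early retreatment are overstated less.* Their unscheduled visit is for recurrence before target, and the visible text does not say how they are counted.
- *Duration is the trial's key efficacy claim.* The documents do not say so.

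**Conclusion.** The point holds for detected losses. After Week 6 the crossing is known only to within 6 and then 4 weeks, and the visible plan names a method that takes it as exact. If events are dated at the detecting visit, the average overstatement is about 2 weeks, and the median is 0 to 4 weeks high depending on where it lies between visits. Using actual dates instead of nominal weeks spreads the medians but leaves the average delay in place. The Kaplan-Meier interval is an interval for time to detection and carries none of the uncertainty about the crossing.

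These sizes rest on assumed distributions, a score without noise and the inferred convention. The existence of the gaps rests on the protocol alone. Absolute duration is affected more than dose comparisons, although on nominal weeks two doses with the same true median can still show medians 4 weeks apart. For a descriptive, non-primary endpoint this is a modest point, worth acting on because the remedy needs only analysis work.

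**What to change.** - State the event-time convention for duration in the SAP.
- Add an interval-censored (Turnbull) estimate by dose from actual assessment dates. The left end is the last visit below target and the right end is the first visit at or above it. Zeros stay at 0, and withdrawals after Week 6 stay right-censored at the last visit. For the Week 36 rollovers, carry in the visit dates from 1720302.
- State how the median is read: either report it as an interval [a, b], or interpolate, for example m = a + (b − a)(S(a) − 0.5)/(S(a) − S(b)). In a check on simulated data, linear interpolation recovered the true median.
- Take the confidence interval from a bootstrap that resamples subjects, since one subject can contribute several cycles.
- Keep the Kaplan-Meier curve for comparison with 1720302, labelled *time to visit at which loss was observed*.

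The cost is SAP wording and one further standard procedure, with no extra visits or data. The reported median will probably be somewhat shorter. Interval censoring corrects for visit spacing and not for early crossings caused by noise, so the two displays should be read together.

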7.2 SUBJECT DISCONTINUATION/WITHDRAWAL FROM THE STUDY

Subjects are free to withdraw from participation in the study at any time with notification.

An investigator may discontinue or withdraw a participant from the study for the following reasons:

- Pregnancy
- Significant study intervention non-compliance (e.g., failure to follow study procedures or to keep follow-up appointments)
- If any clinical AE, laboratory abnormality, or other medical condition or situation occurs such that continued participation in the study would not be in the best interest of the subject
- The subject experiences no reduction or have an increase in the average TWSTRS-total score at Weeks 4 and 6 post-injection relative to the pre-injection TWSTRS-Total score at the beginning of the treatment cycle (i.e., **lack of efficacy**: no improvement or worsened disease status)
- If the investigator determines that another BoNT treatment is needed to control the CD symptoms and less than 12 weeks have elapsed since the last study treatment administration
- If the subject meets an exclusion criterion (either newly developed or not previously recognized) that precludes further study participation

If the subject withdraws consent and discontinues from the study, the investigator will record the reason for consent withdrawal, if one is provided by the subject, in the subject's study records and on the eCRF. If a subject withdraws consent because of an AE, that AE should be indicated as the reason for withdrawal. In the event of early discontinuation, the subject should be asked to return to the study center to complete the assessments specified in the EOS Visit.

If at any time during the study, the investigator determines that it is not in the best interest of the subject to continue, the subject will be discontinued from participation. The investigator can discontinue a subject at any time if medically necessary. Appropriate documentation in the subject's study record and eCRF

regarding the reason for discontinuation must be completed. Prior to discontinuing a subject from study participation, the investigator will discuss his/her intentions with the medical monitor or designee.

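### The zero-duration rule in Protocol 9.6 tests Weeks 4 and 6 separately and sets no minimum response, while peak effect is their average; subjects with no average improvement can keep a non-zero duration

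*Protocol*

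**What the plan says.** Protocol 9.6 defines duration of effect as "time (number of weeks) from treatment until loss of 80% of the peak treatment effect", and takes the peak as "the average of the change from baseline in the TWSTRS-total score at Weeks 4 and 6". Three rules follow.

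- A subject with "no reduction in the TWSTRS-total score at Week 4 and Week 6, his/her duration of effect will be set to 0".
- A subject who "discontinues or withdraws from the study prior or at Week 6, his/her duration of effect will be set to 0".
- For a subject who leaves after Week 6 without reaching target, "his/her duration of effect will be censored at the last visit".

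No minimum size of reduction is stated. The results are Kaplan-Meier curves and medians by dose level.

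Protocol 7.2 describes lack of efficacy as "no reduction or have an increase in the average TWSTRS-total score at Weeks 4 and 6 post-injection relative to the pre-injection TWSTRS-Total score". Protocol 8.1.2.4 also uses the average of the two visits.

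Protocol 4.3 schedules visits at "Weeks 4, 6, 12, and every 4 weeks thereafter until Week 52/End-of-Study Visit", so no visit is scheduled between Weeks 6 and 12. Protocol 8.1.3 allows 6 days either side of the Week 12 visit, and allows unscheduled visits when a subject asks for retreatment. Nothing visible says from which visit loss of effect is assessed.

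**The concern.** The zero rule decides who counts as having had any effect, and the peak decides what must be lost for the effect to end. These should rest on the same quantity, but the first reads as a test of each visit and the second is an average. Two programmers could code the rule differently and report different medians.

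The rule also has no floor. A half-point average fall is treated as an effect, and the schedule then makes Week 12 the next planned opportunity to see it end. The trial is open-label with no control arm, so no comparator shows how much duration visit-to-visit variation alone would produce.

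**Working it through.** The documents give no expected median, SD or power for this endpoint, so there is no figure of theirs to reproduce. The check has two parts.

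**1. The mismatch, without simulation.** Take a pre-injection score of 40, with 39 at Week 4 and 49 at Week 6. The changes are −1 and +9. There is a reduction at Week 4, so the literal rule does not assign 0. The average change is (−1 + 9)/2 = +4, so the peak effect is a worsening. The target, baseline plus 0.2 × average change, is 40 + 0.2 × 4 = 40.8, above baseline. No benefit exists to be lost.

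**2. How often this happens with no true change.** Inputs from Protocol 9.6 and 4.3: visits at Weeks 4, 6, 12 and every 4 weeks to 52; peak = mean of the two changes; event = first score at or above target. Assumptions: normal visit noise, either independent or with 4-week autocorrelation 0.3, 0.6 or 0.8; complete follow-up; baseline not selected for being high. With no mean shift and no ties, the results depend on the correlation and not on the SD.

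Let r be the correlation between the two change scores.

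- Literal rule: P(duration 0) = 1/4 + arcsin(r)/(2π). With independent noise r = 0.5, so 0.25 + 0.5236/6.2832 = 0.333.
- Average rule: P(duration 0) = 0.50 by symmetry.
- If neither visit shows a reduction, the average shows none. So the share with a non-zero duration but no average improvement is 0.50 minus the literal P(0). With independent noise this is 0.50 − 0.333 = 0.167.

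Simulation of 200,000 cycles per model, literal rule, loss counted from Week 12:

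| Noise | r | Set to 0 | Non-zero | Non-zero, average not improved | Still without loss after Week 12 |
|---|---|---|---|---|---|
| Independent | 0.50 | 33.3% | 66.7% | 16.7% | 39.6% |
| Autocorrelation 0.3 | 0.71 | 37.5% | 62.5% | 12.6% | 37.5% |
| Autocorrelation 0.6 | 0.77 | 38.9% | 61.1% | 11.0% | 38.0% |
| Autocorrelation 0.8 | 0.79 | 39.6% | 60.4% | 10.5% | 38.6% |

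More than half of cycles are non-zero, and fewer than half remain after Week 12, so the median is 12 weeks in every row. If a return to target at Week 6 also counts, 48 to 49% remain after Week 6 and the median is 6 weeks.

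Under the average rule, half the cycles are set to 0 and the median is unstable. In 2,000 simulated trials of 350 it was 0 in 51% and 12 weeks in 49%. The literal rule gave 12 weeks in all of them. Rounding scores to whole numbers (mean 40, between-subject SD 10, visit SD 3 to 7) gave 48 to 51% non-zero under the average rule, with a median of 0 at SD 3 and 5 and 12 weeks at SD 7.

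**3. What it takes to reach 16 weeks.** With visit SD 6, loss counted from Week 12 and a non-drug fall of 1 or 2 points, the median was 12 under either rule, except 16 for a 2-point fall with autocorrelation 0.8. A 4-point fall gave 16 to 24. If every retreatment baseline is at or above the subject's true level, the median is 16 under both rules, with 88 to 90% non-zero (literal) or 77 to 79% (average).

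**The case against.** The strongest reply is that the average reading is the natural one, because it matches the peak definition and Protocol 7.2 and 8.1.2.4. A sensible programmer might adopt it unprompted. That supports the correction, since the words as written test two visits. Most of SAP Section 8 is not visible here, so the SAP may already settle the matter. The visible part of SAP Section 10 lists no change to the duration rule, but that is weak evidence.

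A reader might infer that an inert drug would show a median of 12 to 16 weeks. The documents do not support that range. Without a mean change, 12 weeks was the most found, and it needs loss to be assessed from Week 12. Sixteen weeks needs a non-drug fall or a retreatment baseline selected high. The second is plausible if the reading that triggers retreatment is also the new baseline. However, most of the retreatment-visit text is redacted, Protocol 8.1.3 allows 14 days either side of a retreatment visit, and the default baseline in SAP 6.2 is the value before the first dose. With a fresh pre-injection reading, the second-cycle median fell to 0 (average rule) or 6 to 12 weeks (literal rule).

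A reader might also infer that a non-zero duration cannot end before about Week 12. The text does not exclude a Week 6 event, unscheduled visits are possible, and the Week 12 visit may fall at (84 − 6)/7 = 11.1 weeks.

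Finally, the primary endpoints are safety and immunogenicity. Responder rates by dose and cycle, and TWSTRS, CGIC and PGIC by visit, would tend to expose an inert drug. It would be too strong to say that the trial could not tell effect from noise.

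**Conclusion.** The zero rule is wrong as written, because it does not match the peak it serves. Read literally, it gives a non-zero duration to subjects whose average did not improve, about 10 to 17% of cycles with no true effect, for whom the endpoint is undefined.

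The absence of a minimum response is a weaker point. In an unselected cycle with no effect, the literal rule yields a median of up to about 12 weeks, and the average rule one between 0 and 12. A reported median near 12 weeks would therefore say little by itself, while one well above it would still be informative.

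These sizes rest on assumed noise models and complete follow-up. Zeros assigned to withdrawals at or before Week 6 would lower the medians. The correction is worth making, but it concerns a descriptive efficacy summary and not a primary endpoint.

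**What to change.** In Protocol 9.6, and in the SAP if it repeats the rule:

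- Set duration to 0 when the average of the Week 4 and Week 6 changes from that cycle's pre-injection score shows no reduction.
- State the first visit at which loss of effect counts, and whether unscheduled scores can count.
- Report the share of injections set to 0, by dose and cycle, beside each median.

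As an optional supplement, repeat the duration summary with subjects below the trial's own responder cut-off set to 0. That cut-off is not visible in this copy, so no value is proposed here.

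The cost is a few lines of wording and one reported percentage. The supplement adds one table on data already collected and will show shorter durations. Only the analysis changes; the retreatment and withdrawal rules stay as they are.
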